Specific Aim 2: To compare pediatric emergency department clinician acceptability of use of a smartphone otoscope with that of a conventional otoscope, we will assess clinician satisfaction and challenges experienced with each device during the study period with a written questionnaire.

4. Objectives:

To address the specific aims stated above, we will utilize a **randomized control study design** to compare antimicrobial prescribing practices of pediatric emergency department clinicians for encounters in which an otic examination is performed while using the smartphone otoscope to those clinicians using a conventional otoscope. (*Specific Aim 1*). Pediatric emergency care clinicians will be surveyed to assess acceptability of smartphone otoscope use compared to conventional otoscope use during the 6-month study period (*Specific Aim 2*).

5. Study Design and Methods:

We propose a randomized, controlled study. The smartphone otoscope will be used in clinical care in the same manner as a conventional otoscope. Twenty volunteer Pediatric Emergency Department clinicians will be randomized to use either the smartphone otoscope or a conventional otoscope for 6 months for all non-traumatic patient otoscopy (ear examinations). In the event that a clinician assigned to use the smartphone otoscope device is unable to use the assigned smartphone otoscope device, s/he will be able to use a conventional otoscope for the examination that cannot be completed with the smartphone otoscope, with documentation to the study team of the reason that the smartphone otoscope could not be used on a study log. The study log, stored in a locked file cabinet, will be reviewed by a member of the study staff in real time to troubleshoot equipment challenges and to monitor study progression. The option to use a conventional otoscope device by clinicians assigned to use of the smartphone device will ensure that clinical care is not adversely impacted in the event of smartphone device malfunction or another situation that makes smartphone otoscope device not feasible.

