All encounters in which an otic examination is performed for a non-traumatic chief complaint will be considered to be eligible to be included in the study. Eligible encounters will be tracked by having the clinician place a patient identification sticker on a log sheet. The log sheet will contain the physician study ID number, date and times of shift, patient sticker and a notation if a clinician substituted a conventional otoscope for the smartphone otoscope device. The study log sheet will be stored in a locked file cabinet, accessible only to study staff. The electronic medical record will be retrospectively accessed, based on the medical record number listed on the study log sheet to collect study-relevant information (**PED-Oto EMR Abstraction Form**) including age of patient, history of otitis diagnoses, past antimicrobial prescription use, antimicrobial prescribed, duration of antimicrobial prescribed, and instructions given specifying the conditions under which to initiate an antimicrobial, if given. Personal identifiers will be maintained only as necessary to link the encounter to the medical record for extraction of study-related information. All information will be recorded in a password protected electronic database. Paper copies of the study log will be stored in a locked file cabinet. Access to both electronic and paper copies of study information will only be granted to study staff.

Information collected as part of the PED-Oto study:

1. Line listing of patients seen per shift by participating study clinicians and record

of device substitution, **PED-Oto Device Use**.

2. Electronic record medical record review of encounters in which an otoscope device was used as reported by study-participant clinicians. Encounters related to ear trauma will be excluded. The **PED-Oto EMR Abstraction Form** will be completed retrospectively by a member of the study staff.
3. At the conclusion of the 6 month study period, the 10 pediatric emergency department clinicians randomly assigned to use the smartphone otoscope device will complete a written questionnaire to assess their comfort level, ease of use, and preference for or against the otoscope device. This assessment will be known as the **PED-Oto Clinician Assessment**.

6. Participant selection:

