The subjects in this study will be 20 randomly selected pediatric emergency care clinicians who perform care at one or both locations (Egleston or Hughes Spalding) of a tertiary care pediatric hospital system. Subjects will agree to random assignment to either a smartphone otoscope device or a conventional otoscope device for the 6-month study period. Informed consent will be obtained from each participating clinician prior to the initiation of the study by a member of the study staff. Study participants will be asked to: 1) compile a list of patient encounters that included an otoscopic examination for a non-traumatic indication for each shift worked during the study period, 2) document and report episodes of care in which the assigned otoscopic device could not be used on a study-eligible otoscopic examination, 3) the 10 clinicians assigned to use the smartphone otoscope will be asked to complete an end of study assessment, the **PED-Oto Clinician Assessment**.

This study presents no more than minimal risk to the subjects. The greatest risk is the loss of privacy by the participating clinicians. There is likely no direct benefit from participation in the study for the individual clinicians. Clinicians assigned to the smartphone otoscope arm will be permitted to keep the clip-on otoscopic device, without the loaned iPhone, as compensation (approximate retail value \$79) for the time and effort related to instruction of device use and completion of study-related documentation. Clinicians assigned to use a conventional otoscope will be given a \$50 gift card at the completion of the study period. Completion of the 6-month study period will be required for compensation.

7. Statistical analysis:

Statistical analyses will predominantly be descriptive with assessments of means, medians, standard deviations, and statistical tests to correlate device and rates of antimicrobial prescribing practices within and among clinicians. Twenty clinicians (10 assigned to the smartphone otoscope intervention and 10 to conventional otoscopy) will participate in the six month study, with a combined 1000 encounters over the 6-month study period. Allowing for drop out, incomplete data collection and other study related issues, we anticipate that we will have usable assessments from 800 encounters.

8. Adverse event reporting:

As this study does not pose more than a minimal risk to subjects, it is unlikely that there

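### Acceptability is rated only at month 6, with no rating scheduled for a smartphone-arm clinician who stops early, so the result may be biased upwards

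*Combined protocol and SAP*

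**What the plan says.** Acceptability of the assigned device is the third listed study outcome and the subject of Hypothesis 2 and Specific Aim 2. For Aim 2 the protocol says "we will assess clinician satisfaction and challenges experienced with each device during the study period with a written questionnaire".

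The instrument is described twice:

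- Section 5, item 3 of the information collected, sets the timing and the raters: "At the conclusion of the 6 month study period, the 10 pediatric emergency department clinicians randomly assigned to use the smartphone otoscope device". The form covers how comfortable they were with the device, how easy they found it, and whether they prefer it.
- Section 6: "the 10 clinicians assigned to use the smartphone otoscope will be asked to complete an end of study assessment".

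On attrition and incentives:

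- Section 7 reduces 1000 planned encounters to 800 usable ones, with the explanation "Allowing for drop out, incomplete data collection and other study related issues".
- Section 6: "Completion of the 6-month study period will be required for compensation". In the smartphone arm that compensation is the clip-on otoscope itself; in the conventional arm it is a gift card.

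On substitution, section 5 lets a smartphone-arm clinician use a conventional otoscope when the assigned device cannot be used, "with documentation to the study team of the reason that the smartphone otoscope could not be used on a study log". Staff review this log as the study runs, for equipment problems and study progress. The substitution record is listed among the data collected. Section 7 names no analysis of substitutions and none of acceptability.

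**The concern.** A clinician who finds the device unworkable and leaves in, say, month 2 is still one of the 10 assigned. However, no assessment falls at the time of leaving, no later contact is described, and there is no rule for a missing form. That clinician has also lost the compensation and so has little reason to come back and rate. The reward for staying is the device under study, which is plausibly worth least to someone who dislikes it. Missing ratings could therefore be related to opinion.

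With at most 10 raters, one or two missing unfavourable ratings would visibly move the reported result. The error would run in the direction of the study's own hypothesis. A rating not taken at exit may not be recoverable later.

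**Working it through.** **Is there a figure to reproduce?** The documents give no sample size, power or precision figure for acceptability. The only attrition figure is for encounters: 1 − 800/1000 = 20%, or 1000/20 = 50 planned and 800/20 = 40 usable per clinician. That 20% covers several causes together and is not a clinician drop-out rate, so it is not used below.

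**Inputs**

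- Clinicians asked to rate: 10 (sections 5 and 6).
- *a* = number of the 10 who truly favour the device. Assumption, range 5 to 8.
- *d* = number who stop from dislike and are not rated. Assumption, 1 or 2.
- A yes/no favourable rating. Assumption, since the documents define no such endpoint.

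**Formulas**

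- All assigned clinicians rated: *a*/10.
- Rated only if present at month 6: *a*/(10 − *d*).
- Overstatement: *a*/(10 − *d*) − *a*/10 = *a·d* / [10(10 − *d*)].

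**Results**

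| True | One unrated leaver | Overstatement | Two unrated leavers | Overstatement |
|---|---|---|---|---|
| 5/10 = 50% | 5/9 = 55.6% | 5.6 points | 5/8 = 62.5% | 12.5 points |
| 6/10 = 60% | 6/9 = 66.7% | 6.7 points | 6/8 = 75.0% | 15.0 points |
| 7/10 = 70% | 7/9 = 77.8% | 7.8 points | 7/8 = 87.5% | 17.5 points |
| 8/10 = 80% | 8/9 = 88.9% | 8.9 points | 8/8 = 100% | 20.0 points |

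So one such leaver adds about 6 to 9 points and two add 12.5 to 20. In the last row, losing both dissenters removes all recorded dissent.

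**When the bias vanishes.** With *d* = 0 the overstatement is 0, whether because nobody leaves or because leavers still answer. If leaving is unrelated to opinion, it is 0 on average.

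**Sampling error for comparison.** The exact (Clopper-Pearson) 95% interval for 6/10 is 26% to 88%.

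**What the proposed sensitivity result does.** Counting a missing rating as not favourable restores 6/10 = 60% in both 60% scenarios. If the leaver would in fact have been favourable, the month-6 figure is 5/9 = 56% and the sensitivity result is 5/10 = 50%. It is therefore a lower bound, not an estimate.

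**The case against.** Several points on the other side are sound.

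- **The form is addressed to all 10 assigned clinicians.** A reader might infer that the plan restricts the rating to completers. It does not: both descriptions define the group by assignment. What is missing is a procedure for reaching someone who has left.
- **The drop-out wording concerns encounters.** A reader might take it as a forecast that clinicians will leave, or leave from dislike. It gives no clinician rate and no reasons. It shows only that the plan allows for drop-out.
- **Other features work against leaving.** Substitution lets a clinician with device problems stay in the study and rate at month 6, staff troubleshoot as the study runs, and compensation on completion is also an incentive to stay. These lower the chance of the problem but do not remove it.
- **The substitution log is not a hidden acceptability measure.** A reader might infer that the log is ignored, or that it would reveal dissatisfied leavers. Neither is supported. The log is used for troubleshooting and monitoring. Substitution is permitted for malfunction or infeasibility, so a raw count mixes equipment failure with dislike, and it does not record withdrawal. All that can be said is that no acceptability analysis of it is planned.
- **Rating after six months of use is legitimate.** Asking for a preference after extended use is a fair measure; the difficulty is only with those who do not reach that point.
- **The shifts are small beside the sampling error.** True: 7 to 15 points lie well inside 26% to 88%. But this error has one direction and can be reduced without enrolling anyone.

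Sections 8 and 9 also mention real-time reporting of assessment completion and periodic review of the assessments. That wording fits poorly with a single end-of-study form, but it defines no earlier or exit form and so does not close the gap.

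**Conclusion.** The point holds as a conditional risk. There is one rating at the end of month 6, none scheduled for a clinician who stops early, and no rule for missing forms, in a plan that allows for drop-out and compensates only completers. If at least one clinician leaves from dislike and is not rated, reported acceptability would be too high: by about 6 to 9 points for one such clinician and 12.5 to 20 for two, assuming 5 to 8 of 10 truly favour the device and a yes/no rating. None of those inputs is in the documents.

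It would go too far to say that the result is biased. That needs a dislike-related departure without a rating, and the documents do not show that one will occur.

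This is an inexpensive improvement to data collection for a descriptive outcome in 10 people. A separate and larger gap remains: Aim 2 refers to each device, yet only the smartphone arm is surveyed, so the comparison in Hypothesis 2 has no conventional-arm data.

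**What to change.** 1. In sections 5 and 6, schedule the PED-Oto Clinician Assessment at month 6 or when a clinician withdraws or permanently stops using the assigned device, whichever comes first. Record the date and label early-exit ratings as reflecting shorter use.
2. In section 7, report acceptability over all 10 clinicians assigned to the smartphone otoscope, state how many forms are missing, define a favourable rating, and add a sensitivity result that counts missing ratings as not favourable.
3. As supporting information only, tabulate logged substitutions in the smartphone arm by clinician and by reason, keeping malfunction or infeasibility apart from clinician preference.
4. Align the references to clinician assessments in sections 8 and 9 with this schedule.

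The cost is protocol wording, an exit form for the few clinicians who leave, and a table from data already collected. The downside is that early-exit ratings rest on less experience of the device and are not fully comparable with six-month ratings, hence the label. None of this supplies the missing conventional-arm ratings, which need their own change.

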A smartphone otoscope (CellScope-Oto) is a pocket-size attachment that employs the technology and light source of a smartphone to capture reproducible images of the ear canal and tympanic membrane. Previous studies with this device demonstrated that images taken with both the smartphone otoscope and a camera-fitted conventional analogue otoscope were equivalent with respect to image quality (IRB00057321)² and that the smartphone otoscope was acceptable as an educational and diagnostic tool to health professional students (IRB00066495). A pilot study with a similar design to this study conducted in two offices of an ambulatory pediatric clinic demonstrated a trend toward decreased antimicrobial prescription filling among families whose children were examined with the smartphone otoscope (IRB00074526) compared to those who were examined with a conventional otoscope. To further assess this trend, we propose an evaluation of the impact of device use on antimicrobial prescribing for children with an otic complaint in a pediatric emergency department (PED) setting.

We hypothesize that use of a smartphone otoscope with the capability to capture still images and video will reduce the rate of antimicrobial prescribing by emergency department clinicians for otic complaints in children presenting for care in pediatric emergency department settings.

The Pediatric Emergency Department Oto Study (PED-Oto) will be conducted as a

randomized control study in two affiliated children's hospital emergency departments. Twenty volunteer clinicians will be randomly assigned to use either a smartphone otoscope or a conventional otoscope for all otic examinations for a 6-month period. Study outcomes will include:

- 1) rates of antimicrobial prescribing by the clinicians randomly assigned to use a smartphone otoscope compared to the rates of antimicrobial prescribing by the clinicians using a conventional otoscope.
- 2) rates of otitis media or otitis externa diagnoses by the clinicians randomly assigned to use a smartphone otoscope compared to the rates of otitis media or otitis externa diagnoses by the clinicians using a conventional otoscope.
- 3) clinician acceptability of the assigned otoscopic device.

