function and application. A single-center prospective study published in 2015 (IRB00057321)² found that images from the smartphone otoscope device were of comparable quality to those obtained from a camera-fitted device when subsequently reviewed by blinded pediatricians, emergency medicine pediatricians, and an otolaryngologist. The majority felt photographic documentation for diagnosing acute otitis media would reinforce their decision to defer antibiotic administration. A second study assessing acceptability of a smartphone otoscope compared to a conventional wall-mounted otoscope among medical students, nurse practitioner students, and physician-assistant students noted support for the smartphone device for both learning how to conduct the otic exam and for future patient care (IRB00066495). The students concurred that the smartphone otoscope enhanced tympanic membrane view and diagnostic precision, was easy to use, and preferred it over a traditional otoscope when using the devices to examine each other in an educational setting. A study among resident and attending physicians found good correlation between otitis media diagnoses when resident and attending physicians used conventional and smartphone otoscopes in an emergency department setting³. The physicians also agreed that the smartphone otoscope enhanced tympanic membrane view and diagnostic precision, was easy to use, and preferred it over a traditional otoscope. A study conducted in a neurotrauma clinic found a preference for a smartphone otoscope for use in medical education and diagnostic capabilities⁴.

This study has two proposed hypotheses and subsequent aims:

Hypothesis 1: Use of a smartphone otoscope by pediatric clinicians in a pediatric emergency department setting for otic examinations will result in decreased rates of antimicrobial prescribing for presumptive otic infections, compared to rates of providers using a conventional otoscope.

Specific Aim 1: To compare antimicrobial prescribing practices for otitis media among pediatric emergency care clinicians, we will perform a randomized control trial study in which pediatric clinicians will be randomly assigned to use either a smartphone otoscope or a conventional otoscope for 6 months when an otic examination is performed.

Hypothesis 2: Pediatric emergency care clinicians will express a greater acceptability for use of a smartphone otoscope for the examination of children than use of a conventional otoscope.

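### The acceptability questionnaire goes only to the 10 smartphone-arm clinicians, so the device comparison promised in Aim 2 has 10 respondents against none

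*Combined protocol and SAP*

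**What the plan says.** Four statements of intent in the combined protocol and SAP deal with acceptability:

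- Opening summary, study outcome 3: "clinician acceptability of the assigned otoscopic device".
- Section 3, Hypothesis 2: clinicians "will express a greater acceptability for use of a smartphone otoscope for the examination of children than use of a conventional otoscope".
- Section 3, Specific Aim 2, whose stated purpose is comparison: "we will assess clinician satisfaction and challenges experienced with each device during the study period with a written questionnaire".
- Section 4, Objectives: clinicians "will be surveyed to assess acceptability of smartphone otoscope use compared to conventional otoscope use during the 6-month study period".

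Two operational statements say who fills in the form (the PED-Oto Clinician Assessment):

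- Section 5, list of information collected, item 3: "the 10 pediatric emergency department clinicians randomly assigned to use the smartphone otoscope device will complete a written questionnaire". Its purpose is "to assess their comfort level, ease of use, and preference for or against the otoscope device".
- Section 6, third duty of participants: "the 10 clinicians assigned to use the smartphone otoscope will be asked to complete an end of study assessment".

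The questionnaire itself is not in the documents. Section 7 names no analysis of acceptability; the tests it mentions concern prescribing.

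**The concern.** All 20 clinicians have an assigned device, but acceptability is measured in only half of them. If staff follow Sections 5 and 6, Aim 2 produces comfort and ease-of-use ratings for the smartphone otoscope with no reference group. A high rating could not then be told apart from the high rating that clinicians might give any otoscope they had used for six months.

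The one item that could bear on both devices is the preference question. It comes only from clinicians who were given the new device and who keep it if they complete the study, so it is an uncontrolled opinion and not a randomized comparison. Conventional-arm answers that are not collected at the end of the study cannot be fully recovered later.

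**Working it through.** **1. Respondents by arm.** Section 7 gives 10 clinicians per arm, and 10 + 10 = 20 agrees with the stated total. Sections 5 and 6 give the questionnaire to the 10 in the smartphone arm and to none in the conventional arm. That is 10 of 20, or 50% of those randomized. The standard error of a between-arm difference is SD × √(1/10 + 1/n₂). With n₂ = 0 it is undefined, so there is neither an estimate nor an interval.

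**2. Could other records stand in?**

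- The log sheet in Section 5 carries "a notation if a clinician substituted a conventional otoscope for the smartphone otoscope device", and smartphone users must record why the device could not be used.
- Section 6 asks all participants to report examinations where the assigned device could not be used. These entries document some challenges, but not acceptability.
- Sections 8 and 9 mention clinician assessments in general terms. They name no arm and no content, and they set up no conventional-arm survey.

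**3. What the preference item alone could show.** The documents plan no test, so this is an illustration. It assumes a two-way choice between devices, n = 10, and an exact two-sided sign test against 50%.

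- 8 of 10: p = 2 × (45 + 10 + 1)/1024 = 0.109; exact 95% CI 44% to 97%.
- 9 of 10: p = 2 × (10 + 1)/1024 = 0.021; exact 95% CI 55.5% to 99.7%.

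At least 9 of 10 would have to favour one device to reach p < 0.05.

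**4. What surveying both arms would give.** The documents state no alpha, power or SD for acceptability. Assumed here: a roughly continuous score, a two-sample t-test, two-sided alpha 0.05, and 80% power for the detectable difference. The 95% CI half-width, in SD units, is t(0.975, 2n − 2) × √(2/n).

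| Respondents per arm | 95% CI half-width | Difference detectable with 80% power |
|---|---|---|
| 10 | 2.101 × √(2/10) = 0.94 SD | 1.32 SD |
| 8 (assumed non-response) | 2.145 × √(2/8) = 1.07 SD | 1.51 SD |

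With 10 per arm, power is 18.5% for a true difference of 0.5 SD and 56% for 1.0 SD. As a check, the normal approximation gives a detectable difference of (1.960 + 0.842) × √(2/10) = 1.25 SD, a little below the t-test value, as expected at this size.

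**The case against.** The strongest reply is that Hypothesis 2 and the Objectives ask for a comparison of devices without saying that it must be between arms. Smartphone-arm clinicians already know the conventional otoscope, they are asked for a preference, and they may fall back on a conventional device during the study. Earlier studies cited in Section 3 also reported user preference. On this reading a one-arm survey is deliberate, and its appearance in two sections supports that.

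Part of this stands: those two statements, taken alone, can bear a within-user reading. It does not rescue the plan. Outcome 3 concerns the assigned device, and half the clinicians are assigned the conventional one. Aim 2 concerns experience with each device during the study, whereas smartphone-arm clinicians use the conventional otoscope only as a fallback. The described content includes no rating of the conventional device.

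Three smaller objections have some force:

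- The form cannot be seen. Satisfaction and challenges are not named in the summary of its content, but whether the form covers them cannot be verified.
- The power and sign-test figures rest on assumptions that are not in the documents, and the conclusion does not need them.
- Both arms are compensated. Smartphone clinicians keep a device worth about $79 and conventional clinicians receive a $50 gift card, and no effect on responses has been shown. The point about the retained device is therefore a caution, not a demonstrated bias.

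**Conclusion.** The concern holds. The data collection in Sections 5 and 6 contradicts Outcome 3 and Aim 2 directly. It also leaves Hypothesis 2 and the Objectives without a between-arm comparison. The size is 10 respondents against 0, a count taken from the documents that needs no assumption. The prescribing comparison under Aim 1 and patient care are not affected, so this should be fixed but does not threaten the whole trial. Even when repaired, the comparison remains descriptive: under the assumptions stated above, its interval would be about ±0.94 SD.

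**What to change.** **Preferred.** In Sections 5 and 6, have all 20 clinicians complete the same PED-Oto Clinician Assessment about their assigned device at six months, covering comfort, ease of use, satisfaction and challenges. In Section 7, add that the between-arm difference will be reported descriptively with a 95% confidence interval. Also state there that 10 per arm can detect only very large differences (about 1.3 SD at 80% power, with the t-test and alpha assumptions stated). Keep the preference item as a descriptive result for the smartphone arm.

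**Alternative.** If only smartphone-user feedback is wanted, leave Sections 5 and 6 as they are and reword Outcome 3, Hypothesis 2, Aim 2 and the Objectives as a non-comparative assessment by smartphone users.

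**Cost.** The preferred change needs ten more short questionnaires from clinicians who are already to be enrolled and followed, plus small wording changes in Sections 5, 6 and 7. The conventional arm's consent may need updating; the consent pages were not available to check. The alternative costs wording only. Either way, the choice has to be made before the six-month assessment.
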